### **Eligibility Screening and Recruitment**

Eligible breast cancer survivors (n=30) will: a) be ≥ 18 years old, b) be able to speak and read Spanish, c) have no documented or observable disabilities that would interfere with study participation, d) have completed primary treatment for breast cancer (e.g., surgery, chemotherapy, radiation), e) report clinically significant sleep disturbance (i.e., ≥ 8 on the Insomnia Severity Index), f) be at low risk of other sleep disorders that are not amenable to treatment with cognitive-behavioral therapy using the Duke Structured Interview for Sleep Disorders, and g) have access to the Internet and a digital device (e.g., smartphone) capable of using videoconference software.

Potential cancer survivor participants will be recruited from clinics, cancer support groups in the Southern Puerto Rico area, using flyers, postings to online bulletin boards, and via referral from individuals who have heard of the study. All potentially eligible survivors will be approached in a HIPAA-compliant manner by a trained research team member in person and/or via telephone. Those who are approached through medical clinics will be identified in consultation with the medical team. Those who are approached through cancer support groups will be identified in consultation with the cancer support group leader(s). Those who learn of the study via flyers, online postings, or referrals will contact the study team via the telephone number provided to them.

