## Measures

All participants will complete the Pittsburgh Sleep Quality Index, Hospital Anxiety and Depression Scale, and Fatigue Symptom Inventory after consent (i.e., baseline) and after the 6-week intervention (i.e., post-intervention). The post-intervention assessment will also include the Insomnia Severity Index, which will have been administered as part of the screening process. Participants in the intervention group will thus complete two assessments. Participants in the wait-list control group will complete these two assessments (i.e., at baseline and after the 6-week waiting period; i.e., post-waiting) as well as a third assessment after participating in the sessions (i.e., post-intervention). Participants will be sent an e-mail and/or a text message with a link to the follow-up assessment. Participants who have been sent the survey e-mail but have not completed the follow-up survey within 2 days will be contacted up to 3 times to provide any necessary clarifications and/or assistance with completing the survey.

All participants will also complete a 10-item version of the Treatment Perception Questionnaire to assess intervention satisfaction after participating in the sessions (i.e., post-intervention). This validated measure, available in English and Spanish, assesses satisfaction with the intervention, the degree to which participants used the intervention, and the degree to which participants used specific strategies to improve their sleep. Verbal feedback will also be obtained from session participants at the end of each session to identify any terminology that was confusing, or other suggestions for improving the intervention for the future.

Each participant will be sent a \$25 gift card after completing the baseline assessment and a \$75 gift card after completing the post-intervention assessment. Participants randomized to the wait-list group will be provided a \$50 gift card after completing a third assessment after completing an additional assessment after the therapy sessions.

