## Data Analysis

The primary outcomes for this intervention are acceptability and feasibility. The study will be deemed acceptable if  $\geq 50\%$  of eligible cancer survivors who are approached agree to participate and  $> 50\%$  of intervention group participants report that, on average, they agree with positive statements about the intervention (i.e., report an average score of  $\geq 3$  on a scale of 0 to 4). The study will be deemed feasible if  $\geq 75\%$  of the intervention group participants attend at least half of the educational components of the intervention. This will be operationalized as having attended at least half of the sessions. The secondary outcome is sleep disturbance, and efficacy data will be examined at the conclusion of the intervention. Sleep disturbance will be operationalized by scores on the Pittsburgh Sleep Quality Index, sleep efficiency (the percentage of time spent in bed that is spent asleep), and the Insomnia Severity Index. The primary efficacy outcome will be the continuous measures of sleep disturbance. For secondary efficacy analyses, participants will be categorized as having sleep disturbance if 1) their Pittsburgh Sleep Quality Index score is  $\geq 5$  (for subjectively-measured sleep disturbance), 2) if their sleep efficiency is  $<85\%$  (for objectively-measured sleep disturbance), and 3) if their Insomnia Severity Index score is  $\geq 8$ . Although statistical significance will be evaluated, the primary purpose is to compute the effect size at follow-up (Cohen's  $d$ ; difference between groups divided by the pooled standard deviation). Intent-to-treat analyses will be conducted, such that all participants who are randomized will be asked to provide follow-up data at the end of the intervention period regardless of the level of use of the intervention. Participants who do not provide complete follow-up data will not need to have data imputed due to the use of mixed model analyses.

**Aim 4: Explore changes in sleep disturbance during the COVID-19 pandemic which may influence future trials of the new intervention.**

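### The ISI ≥ 8 efficacy category repeats the entry criterion, so the mixed-model reason for not handling missing follow-up does not hold for that one secondary outcome

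*Combined protocol and SAP*

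**What the plan says.** Four statements in the combined protocol and SAP bear on this.

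- **Aim 3, Eligibility Screening and Recruitment.** Survivors must "report clinically significant sleep disturbance (i.e., ≥ 8 on the Insomnia Severity Index").
- **Aim 3, Data Analysis, categories.** The plan says: "For secondary efficacy analyses, participants will be categorized as having sleep disturbance". The third criterion reads "3) if their Insomnia Severity Index score is" 8 or more, the same cut-off as for entry. The continuous measures are the primary efficacy outcome. Acceptability and feasibility are the trial's primary outcomes.
- **Measures.** The ISI is not among the baseline instruments: "The post-intervention assessment will also include the Insomnia Severity Index, which will have been administered as part of the screening process". The screening score is therefore the only pre-treatment ISI. On the number of assessments: "Participants in the intervention group will thus complete two assessments". Wait-list participants complete the same two "as well as a third assessment after participating in the sessions".
- **Aim 3, Data Analysis, missing data.** "Participants who do not provide complete follow-up data will not need to have data imputed due to the use of mixed model analyses". No outcome is exempted, and no model is named for the three categories.

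**The concern.** A mixed model can dispense with imputation when earlier measurements carry information about the missing one. Someone seen only before treatment then still contributes through the correlation between their early and late values. A pre-treatment value that is identical for everyone carries no such information.

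The ISI category is in that position by design. If the missing-data sentence is followed for it, participants without a 6-week score drop out of the comparison while the plan says they are accounted for. Should those lost from the intervention arm be the ones with worse insomnia, the reported proportion no longer meeting the criterion would be too high. In a trial of 30, each such person matters.

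**Working it through.** The plan gives no figure to reproduce. The check asks whether the model is identified, then illustrates the size.

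**Inputs.** From the documents: 30 participants, ISI ≥ 8 for all at screening, the same cut-off at follow-up, and one later ISI before wait-list cross-over. Assumed, because the documents do not give them: 15 per arm, 3 missing per arm, and ISI ≥ 8 at 6 weeks in 5 of 12 observed intervention and 10 of 12 observed wait-list participants.

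**1. Logistic mixed model with screening and 6-week status as responses.** Terms: arm, time, arm × time and a random intercept. All screening responses equal 1, so the likelihood rises as the intercept grows, with the time effect moving to compensate. Each screening term tends to 1, leaving only the follow-up terms. The limiting negative log-likelihood is

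-[5 ln(5/12) + 7 ln(7/12) + 10 ln(10/12) + 2 ln(2/12)] = 13.5571.

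Numerically, with random-intercept SD 1 and the intercept capped at 5 and then 10, the estimate sat on the cap and the value fell from 13.72 to 13.558, towards that limit. There is no finite maximum.

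**2. The random-intercept SD is not identified either.** Each person supplies at most one informative binary value. Every SD tried reaches the same limit, but with a different arm contrast at follow-up:

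| SD | Limiting value | Follow-up log odds ratio |
|---|---|---|
| 0.01 | 13.5571 | -1.95 |
| 1 | 13.5571 | -2.31 |
| 2 | 13.5571 | -3.12 |
| 4 | 13.5571 | -5.16 |

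**3. Dropouts add nothing.** At SD 1, all 30 participants and the 24 completers give the same likelihood and the same log odds ratio (-2.312).

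**4. A linear mixed model on the 0/1 outcome does run,** with a boundary warning. Its arm × time estimate is -0.4167, exactly the completers' difference: 5/12 - 10/12 = -0.4167. Dropouts have the same screening value as completers, so there is nothing to adjust.

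**5. What the six missing values could do.**
- Intervention missing all below 8, wait-list missing all ≥ 8: 5/15 - 13/15 = -0.53.
- The reverse: 8/15 - 10/15 = -0.13.
- Each missing person moves the difference by 1/15; six span 6/15 = 0.40.

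**6. A follow-up model can be fitted.** Log odds ratio ln[(5/7)/(10/2)] = -1.95; SE √(1/5 + 1/7 + 1/10 + 1/2) = 0.97.

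**7. What the screening score recovers.** In a large simulation (200,000 people, all inputs assumed), screening ISI was normal with mean 15 and SD 5, truncated at 8. Follow-up ISI was 14 + 0.6 × (screening - 15) - 5 if in the intervention arm, plus error with SD 4. Intervention dropout rose with screening ISI (28.9% missing); wait-list dropout was unrelated to it (20.1% missing).

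| | Risk difference |
|---|---|
| Truth | -0.296 |
| Category only (completers) | -0.362 |
| Adjusted for screening ISI score | -0.295 |

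The completers' result exaggerates the effect by 0.362 - 0.296 = 0.066. With dropout unrelated to ISI in both arms, both estimates were -0.295.

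**The case against.** The strongest reply is that the plan never commits the categories to a repeated-measures logistic model. The Data Analysis section looks at efficacy when the intervention ends and puts the effect size at follow-up first, so a 6-week comparison by arm fits its wording. Hypothesis 2, on pre- to post-treatment reductions, points the other way, so the text is ambiguous. This reply stands as far as fitting goes: a reader might infer that the ISI analysis cannot be run or will fail to converge, and the documents do not support that. It does not rescue the missing-data sentence. A follow-up-only comparison of the category is also a completers' comparison, with no mixed model to lean on.

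Three further replies have force.

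- A reader might infer that imputation is therefore required. It is not: the continuous screening score is already collected, and adjusting for it is valid without imputation if missingness depends only on arm and that score. What fails is the reason given.
- A reader might infer that the plan breaches its own intent-to-treat rule. The plan defines that rule as asking all randomised participants for follow-up data, whatever their use of the intervention; analysing what is returned does not contradict it.
- The wait-list arm's third assessment gives that arm a second value that can vary. But it follows cross-over and exists in one arm only, so it supplies no randomised comparison.

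**Conclusion.** The point holds for one outcome. The ISI category is constant before treatment by eligibility, so the stated justification for leaving missing follow-up unhandled is untrue for it. This follows from the text and needs no assumption about dropout. The size does: with 3 of 15 missing per arm, the difference could lie anywhere within a 40-point range, and in the simulation severity-related dropout exaggerated the effect by about 7 points. If dropout is unrelated to ISI there is no bias, and with no dropout the issue disappears.

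The reach is limited. This is one of three categories in a secondary efficacy analysis of a 30-person pilot. The continuous measures keep their mixed-model rationale. PSQI ≥ 5 and sleep efficiency below 85% are not fixed by the entry criterion, so the argument does not extend to them. The acceptability and feasibility criteria do not use the ISI category. It should be corrected because the remedy uses data already collected, but it does not threaten the pilot's main conclusions.

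**What to change.** In the Aim 3 Data Analysis section:

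1. Limit the mixed-model rationale for missing data to outcomes whose pre-treatment value varies between participants.
2. State that ISI ≥ 8 status is compared between arms at the 6-week assessment only, before wait-list participants cross over. Report a risk difference with 95% CI from a model adjusted for the continuous screening ISI score, standardised over everyone randomised. Confirm that the wait-list post-waiting assessment includes the ISI, as the Measures section implies.
3. Report the number missing in each arm, with missing counted as still ≥ 8 as a sensitivity analysis.

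Item 3 should not be the main rule, because it is a single imputation with its own bias. Suppose 60% v 20% truly fall below 8 and 20% drop out at random in each arm. It then reports 0.8 × 60 = 48% v 0.8 × 20 = 16%, a difference of 32 points instead of 40. With dropout in the intervention arm only, it reports 48 - 20 = 28 points.

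The cost is a few sentences and a little more analysis work. The adjusted estimate relies on missingness depending only on arm and screening ISI, which the data cannot confirm.

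### Cohen's d at follow-up is defined without a baseline term or a link to the mixed model; a baseline-adjusted d would be more precise if r exceeds about 0.2 and resists baseline-related dropout

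*Combined protocol and SAP*

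**What the plan says.** All references are to the combined protocol and SAP, mostly its Aim 3 sections.

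- **Rank of the output.** Data Analysis states: "The primary outcomes for this intervention are acceptability and feasibility". Sleep disturbance is the secondary outcome, measured by the PSQI, sleep efficiency and the ISI. Within that efficacy analysis, significance will be evaluated, but "the primary purpose is to compute the effect size at follow-up".
- **Definition of d.** The only definition is "difference between groups divided by the pooled standard deviation". It does not say whether the means are observed or model-based, or which SD is pooled.
- **Mixed model.** It is mentioned once, in Data Analysis: participants with incomplete follow-up "will not need to have data imputed due to the use of mixed model analyses". Its fixed effects, its handling of baseline and its relation to d are not given.
- **Baseline data.** Measures provides for a PSQI before randomization ("All participants will complete the Pittsburgh Sleep Quality Index, Hospital Anxiety and Depression Scale, and Fatigue Symptom Inventory after consent (i.e., baseline"). The ISI is repeated at post-intervention, and its earlier value is the one "which will have been administered as part of the screening process".
- **Assessment times.** Wait-list participants are assessed at baseline and after the waiting period, "as well as a third assessment after participating in the sessions (i.e., post-intervention".
- **Hypothesis.** Hypothesis 2 in Specific Aims concerns reductions from before to after treatment, not follow-up level alone.

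**The concern.** Three estimators fit this text: the raw follow-up difference, a difference in change scores (suggested by Hypothesis 2) and a model-based contrast. The wording of the definition points to the first. They differ in precision, and nothing fixes the choice before the data are seen.

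A d from observed follow-up scores has two weaknesses. It leaves out the baseline information, which matters with about 15 per arm. It is also a statistic of those who returned the follow-up survey, so the argument that the mixed model makes imputation unnecessary does not cover it. Differential dropout is conceivable, because only the intervention arm attends six weekly sessions before the 6-week assessment.

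The plan ranks this d above significance testing, so its interval and its freedom from avoidable bias deserve a sentence of specification.

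**Working it through.** **Inputs.** From the plan: N = 30, two arms, ISI of at least 8 for entry. The plan gives no allocation ratio, correlation, SD or dropout rate. Assumed: 15 per arm, unit SD, true difference 0.5 SD in favour of the intervention, and r (the within-trial baseline/follow-up correlation) from 0 to 0.7. The plan has no effect-size or power figure to reproduce.

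**1. Precision with complete data.**

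- Unadjusted SE of the difference = sqrt(2/15) = 0.365; 95% half-width 1.96 × 0.365 = 0.72.
- Adjusted SE (ANCOVA) = 0.365 × sqrt((1 − r²)(1 + 1/26)).
- Break-even: (1 − r²)(27/26) = 1, so r = sqrt(1/27) = 0.19.

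| r | Adjusted SE | 95% half-width | Variance ratio, unadjusted/adjusted |
|---|---|---|---|
| 0 | 0.372 | 0.73 | 0.963 |
| 0.2 | 0.365 | 0.71 | 1.003 |
| 0.3 | 0.355 | 0.70 | 1.058 |
| 0.5 | 0.322 | 0.63 | 1.284 |
| 0.7 | 0.266 | 0.52 | 1.888 |

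These half-widths treat the SD as known. Simulating d itself, with the SD estimated (20,000 trials per setting), gives a sampling SD of 0.38–0.39 for raw d. For adjusted d it is 0.40, 0.38, 0.38, 0.34 and 0.29 at the five values of r.

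With N completers the break-even is sqrt(1/(N − 3)): 0.21 at 26 and 0.24 at 20.

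The variance of a change-score difference relative to raw is 2(1 − r): 1.40, 1.00 and 0.60 at r = 0.3, 0.5 and 0.7. The adjusted contrast has 0.945, 0.779 and 0.530, so it is better than change scores at each of these values.

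**2. The ISI.** Participants must "report clinically significant sleep disturbance (i.e., ≥ 8 on the Insomnia Severity Index", which narrows the baseline range. Assume a normal screening score with SD 5.5 and mean 10 to 14, cut at 7.5 because scores are integers. The baseline SD then falls to a share u = 0.688 (mean 10) or 0.827 (mean 14) of its unselected value. Within-trial r = ru / sqrt(1 − r² + r²u²).

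| Unselected r | Within-trial r | Gain, as extra participants |
|---|---|---|
| 0.3 | 0.21–0.25 | 1–3% |
| 0.5 | 0.37–0.43 | 12–18% |
| 0.7 | 0.56–0.63 | 40–60% |

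**3. Dropout explained by baseline.** Simulation with 15 per arm and 20,000 trials per setting. Intervention dropout is 20% with a logit slope on baseline of +1.2 (more severe patients leave) or −1.2; control dropout is 5% at random. Both d's are divided by the raw pooled follow-up SD. The no-bias reference is about 0.515, because d is slightly inflated in small samples.

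| r | Raw d, slope +1.2 / −1.2 | Adjusted d, slope +1.2 / −1.2 |
|---|---|---|
| 0 | 0.52 / 0.52 | 0.51 / 0.52 |
| 0.2 | 0.56 / 0.48 | 0.51 / 0.52 |
| 0.3 | 0.58 / 0.46 | 0.52 / 0.52 |
| 0.5 | 0.62 / 0.42 | 0.52 / 0.52 |
| 0.7 | 0.67 / 0.39 | 0.53 / 0.52 |

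The shift of raw against adjusted d is about 0.10 at r = 0.5 and 0.14 at r = 0.7. The sampling SD of raw d is about 0.42. At r = 0.5, slopes of ±0.5 give a shift of about 0.05.

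**4. Variations at r = 0.5, slope +1.2.**

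- Same slope and 12.5% dropout in both arms: raw 0.52, adjusted 0.52.
- Same slope in both arms, 20% against 5% dropout: raw 0.60, adjusted 0.52.
- Slope in the intervention arm only, 10% against 5% dropout: raw 0.57, adjusted 0.52.

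**5. What adjustment does not cure.** If intervention dropout depends on the follow-up score itself (slopes ±1.2, r = 0.5), raw d is 0.742 / 0.325 and adjusted d 0.695 / 0.372. The share of bias remaining is (0.695 − 0.515)/(0.742 − 0.515) = 0.79 in one direction and (0.515 − 0.372)/(0.515 − 0.325) = 0.75 in the other.

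**6. Choice of SD.** Dividing the adjusted difference by the residual SD changes the scale: at r = 0.5 mean d rises from about 0.51 to 0.60. It also cancels the precision gain: the sampling SD of d is 0.40, against 0.39 for raw d and 0.345 for adjusted d over the raw pooled SD.

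**The case against.** The best defence is that this is under-specification and not a wrong choice. The plan commits to mixed models, frames its hypothesis as change and measures the PSQI before and after. The parenthesis on d may be only the textbook gloss. That stands to this extent: a model-based d is not excluded, and the plan does not contradict itself. But nothing links d to the model, and the definition as written has no baseline term.

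The bias also depends on the scenario. When the baseline–dropout relation and the dropout rate match across arms, raw d is not shifted. Lower dropout halves the shift, and the plan provides up to three reminder contacts. Adjusted d is protected only if the baseline relation is roughly linear and missingness does not depend on the unseen outcome. All of this stands as a limit on size. Equal slopes alone are not enough, as the 20% against 5% case shows.

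The precision gain rests on assumed correlations and is modest for the ISI. Delivery in groups of up to 10 adds variance that baseline cannot remove: with an assumed ICC of 0.05 and groups of 7–8, the 28% gain at r = 0.5 falls to about 23%. With 20 completers the cost at r = 0 is 1/16, about 6%, and not 4%. These points reduce the benefit without reversing it.

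Finally, no pilot success criterion depends on d. That is correct and limits the priority.

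**Conclusion.** The concern holds. The main efficacy output is defined without baseline and without a tie to the mixed model, although the plan already collects what a better estimator needs. On the assumption of 15 per arm and 30 completers, adjustment pays once within-trial r passes 0.19. At r = 0.5 it narrows the 95% half-width from 0.72 to 0.63. It also removes a shift of about 0.05 to 0.10 (r = 0.5) under the dropout patterns examined in which baseline drives intervention-arm losses only. It does not rescue the estimate from dropout driven by unseen follow-up scores.

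The text and the algebra are secure; the size of the benefit is not, because the documents give no correlation, dropout rate or allocation ratio. The change should be made because it is cheap, but it concerns a secondary output and does not threaten the trial's primary feasibility and acceptability conclusions.

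**What to change.** In Aim 3, Data Analysis, replace the definition of d for every continuous sleep measure that has a pre-randomization value (for the ISI, the screening score):

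- **Contrast:** the baseline-adjusted difference at the 6-week assessment, intervention post-intervention against wait-list post-waiting. The wait-list group's third assessment does not enter.
- **Model:** the planned mixed model with baseline means constrained equal between arms, or ANCOVA.
- **Divisor:** the raw pooled follow-up SD, not the residual SD.
- **Reporting:** a 95% CI, with the same contrast used for the significance test. Raw follow-up d may be shown descriptively.
- **Assumption:** state that the estimate takes missingness to be explained by arm and baseline.

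The plan does not state the data source for sleep efficiency. If it has no pre-randomization value, this definition cannot apply to it and the plan should say so.

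The cost is one or two sentences, with no new data, participants or procedures. The statistical price is about 4% more variance if baseline and follow-up are uncorrelated (about 6% with 20 completers).
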